T _{max}	The time to reach the maximum concentration after drug administration [time]
V _L	Volume of distribution
V _{ss}	The volume of distribution at steady state following intravenous administration [volume]
V _{z/F}	The apparent volume of distribution during the terminal elimination phase following extravascular administration [volume]

Glossary of terms

Assessment	A procedure used to generate data required by the study
Cohort	A specific group of patients fulfilling certain criteria
Control drug	Any drug(s) (an active drug or an inactive drug, such as a placebo) which is used as a comparator to the investigational drug being tested in the trial
Dosage	Dose of the study treatment given to the patient in a time unit (e.g. 100 mg once a day, 75 mg twice a day)
Electronic Data Capture (EDC)	
Electronic data capture (EDC) is the electronic acquisition of clinical study data using data collection systems, such as Web-based applications, interactive voice response systems and clinical laboratory interfaces.
 
EDC includes the use of Electronic Case Report Forms (eCRFs) which are used to capture data transcribed from paper source forms used at the point of care.

Enrollment	Point/time of patient entry into the study at which informed consent must be obtained (i.e. prior to starting any of the procedures described in the protocol)
Epoch	Interval of time in the planned conduct of a study. An epoch is associated with a purpose (e.g. screening, randomization, treatment, follow-up) which applies across all arms of a study.
Investigational drug	The study drug whose properties are being tested in the study; this definition is consistent with US CFR 21 Section 312.3 and Directive 2001/20/EC and is synonymous with “investigational new drug,” “Investigational Medicinal Product,” or “test substance”
Patient	An individual with the condition of interest
Randomization number	A unique identifier assigned to each randomized patient, corresponding to a specific treatment arm assignment
Screen Failure	A patient who is screened but is not treated or randomized
Source Data/Document	Source data refers to the initial record, document, or primary location from where data comes. The data source can be a database, a dataset, a spreadsheet or even hard-coded data, such as paper or eSource

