3.1 Study design

Figure 3-1 Study Design

This is a non-confirmatory, randomized, patient and investigator-blinded, placebo-controlled, parallel-group study in patients with PAD and intermittent claudication. Approximately 40 randomized patients will be treated in a 1:1 ratio to receive LLG783 or placebo as an i.v. infusion of CCI i.v. dosing once every 4 weeks for a total of 4 doses over a period of 12 weeks/3 months. Key study assessments are conducted at week 16 (month 4) of the study (i.e. after 16 weeks of exposure), which is one month after the final dose of study medication.

The dose may be altered based on review of data from the 1st interim analysis (IA).

Corporate Confidential Information

Potential study participants will undergo screening assessments, including 6MWT and ABI, to determine eligibility. Patients who pass the screening evaluations will come to the investigational site on Day 1, at which time inclusion and exclusion criteria will be re-reviewed, and eligible patients will be randomized and dosing will commence.

Assessments of functional capacity (6MWT) will be made at weeks 8 and 16 (days 57 and 113) following the first dose of study medication, with follow-up functional assessments at weeks 24 and 32 (days 169 and 225) following the first dose of study medication (i.e. 2 and 4 months following the last dose of medication, see [Figure 3-1](#)). These follow-up assessments will be performed to help define durability of clinical response as LLG783 exposure declines. The primary endpoint of improved walk distance will be adjudicated based on the 8 and 16 week data points, though the 24 and 32 week data may be used in final statistical modeling.

Safety assessments will include physical examinations, ECGs, vital signs, standard clinical laboratory evaluations (hematology, blood chemistry, and urinalysis), as well as AE and SAE monitoring.

Patients who discontinue the study for reasons other than safety prior to the week 16 visit may be replaced in order to ensure ability to assess 40 patients with a functional assessment after 16 weeks of exposure.

Corporate Confidential Information

Corporate Confidential Information

Corporate Confidential Information

Corporate Confidential Information

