 - h. Uncontrolled diabetes as defined by a random fasting glucose level of 13 mmol/L or 240 mg/dL or a HbA1c greater than 9% as measured at screening. Diabetes should be treated as appropriate during the study.
6. Any of the following concomitant hepatic or renal conditions or diseases:
 - a. Patients with severe renal impairment defined as eGFR < 15 mL/min/1.73m² [as calculated by the MDRD (Modification of Diet in Renal Disease) method] or those receiving current or planned dialysis or ultrafiltration.
 - b. Known active or recurrent hepatic disorder (including cirrhosis, hepatitis B and hepatitis C - including positive hepatitis B surface antigen or hepatitis C test), or alanine aminotransferase/aspartate aminotransferase (ALT/AST) levels > 2.5 times upper limits of normal (ULN) or total bilirubin > 2 times ULN at screening.
7. History of any of the following chronic conditions:
 - a. Malignancy of any organ system (other than localized basal or squamous cell carcinoma of the skin), treated or untreated, within the past **3 years**, regardless of whether there is evidence of local recurrence or metastases.
 - b. Hemoglobin levels < 10.6 g/dL at screening.

- c. History of immunodeficiency diseases, including a positive HIV (ELISA and Western blot) test result.
 - d. History of any hypercoagulable or bleeding disorders.
8. Major surgical procedure (such as coronary artery bypass grafting, carotid endarterectomy, abdominal surgery) \leq 6 months before screening (\leq 4 weeks before screening for coronary stent placement or angioplasty) or planned coronary revascularization or any other major surgical procedure planned to occur during the planned time frame of the study. Patients who have undergone peripheral vascular interventions $>$ 6 months prior to screening may still be considered eligible, provided they meet all other inclusion/exclusion criteria. Patients with actively planned/scheduled lower extremity peripheral vascular interventions within the first 4 months after enrollment should not be enrolled. However, if clinically indicated during the study, a patient may undergo peripheral vascular intervention.
 9. Any surgical or medical condition that in the opinion of the Investigator may place the patient at higher risk from his/her participation in the study.

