7.2 Discontinuation of study treatment

Patients may voluntarily discontinue study treatment for any reason at any time.

The investigator should discontinue study treatment for a given patient if, on balance, they believe that continuation would be detrimental to the patient's well-being.

Study treatment MUST BE discontinued for a given patient under the following circumstances:

- Patient withdraws consent
- Pregnancy
- Severe hypersensitivity reaction occurs, including any of the following: anaphylaxis, fever, chills, urticaria, dyspnea, headache, myalgia, hypotension. Immediate interruption of the infusion to administer study treatment is required in such cases if the reaction occurs during infusion.
- Circumstances where the Sponsor or investigator determine that continuation of treatment puts the patient's safety at significant risk.

There may also be situations where the patient's safety is not considered to be at risk, but where study treatment may be temporarily suspended at the discretion of the investigator, such as:

- A protocol deviation (missed assessment, use of prohibited medication)
- Lab value for individual patient is outside the normal range

Under these circumstances, the Investigator may choose to hold study drug pending further investigation and collection of additional data, or discussion with the Sponsor. If after such deliberation, the Investigator deems the study drug safe to be restarted at a time point which is outside the treatment window for that dose, the patient should skip the interrupted dose and restart dosing at the next dose (unless this is the final dose, in which case, no further doses should be given). This missed dose should be reported in the CRF by the investigator. No replacement dose should be given (i.e. there should be no dosing beyond the scheduled month dosing window) to avoid exposure longer than that study in the 13-week GLP toxicology study.

All visits, including dosing visits, should be scheduled as per the study assessment table (see the SOM for visit windows).

In case of an unavoidable delay in dosing visits, the site may still dose a patient if the visit is ≤ 7 days later than the scheduled timepoint. Dosing visits which exceed a 7-day delay should be considered as missed doses. All other scheduled assessments should still take place as per the protocol assessment table for that visit, despite the duration of the delay.

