The subsequent visit should, as much as possible, continue to be scheduled as per the original planned visit schedule (i.e. the subsequent visit should NOT be delayed by the same number of days as the delayed dosing visit).

The exception to this request is for the fourth dose. If the fourth (final) dose is delayed, then the week 16 visit should also be delayed by approximately the same number of days to ensure approximately one month between final dose and the week 16 assessments.

Patients who miss more than 1 dose should be discontinued from the study, but should continue to return for safety assessments.

The appropriate personnel from the site and Novartis will assess whether study treatment should be discontinued for any patient whose treatment code has been broken inadvertently for any reason.

If discontinuation of study treatment occurs, the investigator must determine the primary reason for the patient's premature discontinuation of study treatment and record this information on the Dosage Administration CRF.

Patients who discontinue study treatment should NOT be considered withdrawn from the study UNLESS they withdraw their consent (see [Section 7.3](#), Withdraw of Informed Consent). Where possible, they should return for the assessments indicated by an asterisk (*) in the [Assessment Schedule](#).

If they fail to return for these assessments for unknown reasons, every effort (e.g. telephone, e-mail, letter) should be made to contact the patient/pre-designated contact as specified in [Section 7.4](#) (Lost to follow-up). This contact should preferably be done according to the study visit schedule.

The investigator must also contact the IRT to register the patient's discontinuation from study treatment.

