11.4.3 Handling of missing values/censoring/discontinuations

The primary analysis will be based on all patients with a baseline MWD and at least one post-baseline MWD. Patients who undergo any lower extremity vascular interventions (angioplasty, stenting, or bypass surgery) before the Week 16 efficacy assessment or patients who drop out for other reasons before this assessment may be replaced to ensure 40 patients complete this primary endpoint assessment. Data from such patients will be included in the model for the primary analysis until the time of dropout or intervention; no imputation of the missing data will be performed for the primary analysis.

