6.1.1 Variables

The primary efficacy endpoint is the Maximum walking distance (MWD) defined as the total distance walked in 6 minutes as assessed by the 6MWT and will be used to evaluate functional capacity of PAD subjects participating in this study.

Change from baseline in MWD will also be derived. Baseline will be taken from the screening 6-minute walk test.

6MWT data will be excluded from primary and secondary analyses under below conditions:

- within 24 hours after narcotic pain medication
- the very first 6MWT after the adverse event of COPD exacerbation
- all tests after post baseline stent or angioplasty procedures
- Lap distance for the 6MWT significantly shorter than the recommended length of 50-70m

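### Exclusion criterion 8 ties the bar on planned leg interventions to enrollment rather than to the Week 16 walk test, which on the glossary's definition leaves a short uncovered gap for patients who consent early in screening

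*Protocol*

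**What the plan says.** Protocol 4.2, criterion 8, gives planned leg revascularisation its own sentence: "Patients with actively planned/scheduled lower extremity peripheral vascular interventions within the first 4 months after enrollment should not be enrolled". The same criterion bars planned coronary revascularisation and other planned major surgery for the whole study, and lets a patient have a leg intervention during the study if it becomes clinically indicated.

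The protocol glossary defines enrollment as "Point/time of patient entry into the study at which informed consent must be obtained". Table 8-1 places consent at the screening visit, between Day -21 and Day -2.

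Protocol 3.1 says that the walk tests are "made at weeks 8 and 16 (days 57 and 113) following the first dose of study medication". Under Protocol 7.2, "the site may still dose a patient if the visit is ≤ 7 days later than the scheduled timepoint". If it is the fourth dose that is late, "then the week 16 visit should also be delayed by approximately the same number of days".

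On analysis, Protocol 11.4.3 covers patients who have a leg intervention before Week 16: "Data from such patients will be included in the model for the primary analysis until the time of dropout or intervention". Nothing is imputed in the primary analysis. SAP 6.1.1 removes "all tests after post baseline stent or angioplasty procedures" from the primary and secondary analyses. Both efficacy criteria (Protocol 11.4.2, SAP 6.1.3) are read at Week 16.

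**The concern.** A bar on planned leg procedures protects the primary endpoint only if it lasts until that endpoint has been measured. Here the bar is a fixed number of months counted from enrollment, while the endpoint is fixed relative to the first dose. If enrollment is consent, up to three weeks of screening come off the protection at the far end, and a late fourth dose takes off up to another week.

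No other rule clearly fills the gap. The clause on planned major surgery may well catch an open bypass, but it does not clearly reach a leg stent or angioplasty, which has its own sentence. Criterion 9 concerns risk to the patient, not loss of the endpoint. Investigators are told not to add exclusions of their own (Protocol 4 and 4.2), and the Day 1 re-check applies the same criterion with the same clock.

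At stake is a missing value at the only visit used for both success criteria, arising from a procedure whose date was already known when the patient was screened.

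**Working it through.** **Day count.** There is no Day 0 in the count used here, so the interval from Day -s to Day d is s + (d - 1). Two checks against the protocol's own figures:
- Day 1 to Day 113 = 112 days = 16.0 weeks, as in Protocol 3.1.
- Day -21 to Day 225 = 21 + 224 = 245 days = 35.0 weeks, matching the roughly 35 weeks in Protocol 3.7.1.

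**Length of the window.** Four calendar months, taken from every start date in a four-year cycle, last 120 to 123 days. Protocol 3.1 also equates week 16 with month 4. On that convention four months are 4 × 28 = 112 days.

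**Time from the start of the clock to the Week 16 walk test**, and the part left uncovered (time minus window):

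| Clock starts | Week 16 visit | Days to Week 16 | Gap, calendar months | Gap, 4-week months |
|---|---|---|---|---|
| Consent, Day -21 | on time | 21 + 112 = 133 | 10-13 | 21 |
| Consent, Day -21 | dose 4 late by 7 days | 133 + 7 = 140 | 17-20 | 28 |
| Consent, Day -2 | on time | 2 + 112 = 114 | none | 2 |
| Consent, Day -2 | dose 4 late by 7 days | 114 + 7 = 121 | 0-1 | 9 |
| Day 1 | on time | 112 | none | none |
| Day 1 | dose 4 late by 7 days | 112 + 7 = 119 | none | 7 |

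If a Day 0 were counted, the intervals from consent would each be one day longer.

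**When the gap opens (consent clock, calendar months).** On time, it needs s + 112 > 120, so consent on or before Day -9, or s + 112 > 123, so on or before Day -12. With the full 7-day delay it needs s + 119 > 120 or > 123, so consent on or before Day -2 or Day -5.

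**Example.** A patient consents on Day -21 and has a leg stent booked 125 days later. That is beyond 123 days, so criterion 8 does not apply. The stent falls on Day 105 (125 - 21 = 104 days after Day 1), before the Day 113 walk test. The Week 16 value is then excluded, and a Week 8 value from Day 57 is kept.

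**The case against.** The strongest reply is that enrollment in criterion 8 does not mean consent. The criterion itself says that such patients should not be enrolled, yet they must have consented before anyone can assess them. Protocol 4 treats enrollment as something that an entry-criterion deviation prevents. Criterion 15 speaks of confirming whether a patient reviewed at screening can be enrolled, and Protocol 6.11 contrasts the time before randomization with the time after enrollment. The protocol summary enrolls about 40 patients where Protocol 4 randomizes about 40. Four months also matches the protocol's label for week 16, which suggests a clock from Day 1. On that reading with calendar months the gap is zero. This stands as a serious alternative. It does not dispose of the point, because it contradicts the glossary, sites could apply either reading, and with 4-week months a delayed visit would still fall up to 7 days outside.

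A reader might also infer that 133-140 days is the usual interval, or that each case costs one of about 40 primary assessments. The documents support neither:
- 133 days is the earliest-consent case, and 140 days needs the full dose-4 delay as well. That delay cannot be foreseen at screening.
- Protocol 4 says that patients who need an intervention before Day 113 will be replaced. Protocol 3.1 and 11.4.3 say that replacement may occur, with the aim of 40 patients assessed at Week 16. The cost of a case is then one extra recruit, and the Week 8 value still contributes to the repeated-measures model.

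Finally, the protocol does not state why criterion 8 uses four months, so its purpose of protecting the endpoint is an inference.

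**Conclusion.** The point holds as a narrow gap that depends on how enrollment is read. Given the glossary definition, criterion 8 can admit a patient whose leg stent or angioplasty is already scheduled before the Week 16 walk test. Three conditions must coincide: consent early in screening, a procedure booked about four months ahead, and a date inside the short slot calculated above.

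The documents give no rate of such bookings, so the number of patients cannot be estimated; it is likely to be small. No effect on power was calculated, since the sample-size section is not in the public text. Footnote 1 to the screening column of Table 8-1 and the visit windows in the Site Operations Manual are also unavailable, and either could change the interval.

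It would go too far to conclude that the trial is exposed to a material loss of primary data. What the documents support is an ambiguous clock that permits an occasional avoidable missing value at the decisive visit. It is worth correcting because the correction is so cheap.

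**What to change.** Anchor criterion 8 to the endpoint: exclude patients who already have a lower-extremity vascular intervention planned to occur before their Week 16 (Day 113) 6MWT, allowing for the permitted dose-4 delay (113 + 7 = Day 120). Sites can project the date at screening and confirm it at the Day 1 eligibility review that Protocol 4 already requires. The allowance for a clinically indicated intervention during the study stays as it is.

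This matches the rest of the protocol, which already refers to Week 16 for replacement (Protocol 4), for restricted changes in pain and PAD symptom drugs (Table 5-1) and for missing-data handling (Protocol 11.4.3). It also removes the need to settle, for this criterion, what enrollment or a month means.

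The cost is one phrase in an amendment, plus a few patients with a procedure booked in the gap who become ineligible. For sites that already count from Day 1 in calendar months almost nothing changes: the protected period would be 119 days against 120-123 now.

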5.1 Contraception requirements

Women of child bearing potential must be informed that taking the study treatment may involve unknown risks to the fetus if pregnancy were to occur during the study, and agree that in order to participate in the study they must adhere to the contraception requirement outlined in [Section 4.2](#) (Exclusion Criteria).

If there is any question that the patient will not reliably comply, they should not be entered or continue in the study.

Women who become pregnant during the study should NOT be administered any further doses of study drug. Refer to [Section 9.6](#) for Pregnancy Reporting requirements.

5.2 Prohibited treatment

Use of the treatments displayed in [Table 5-1](#) is NOT allowed throughout the prohibited period noted in the table.

Table 5-1 Prohibited medication

Medication	Prohibited period	Action to be taken
Monoclonal antibody use must be reported to the Novartis study safety monitor to be reviewed before a patient can be enrolled or continued in this study.	Within 6 months of screening through to the end of the study	Novartis safety monitor may exclude patient from study or require discontinuation of study treatment in cases where highly similar classes/types of antibodies are prescribed (and replacement of patient in study)
Change in type or dosage of narcotic pain relievers; OR Change in type or dosage of PAD specific symptom-relief drugs (specifically: cilostazol, pentoxifylline, or naftidrofuryl)	4 weeks prior to screening through week 16	Notify Novartis study team as it may be determined that it is necessary to discontinue study treatment and replace the patient

5.3 Dietary restrictions and smoking

Not applicable.

Smoking and alcohol history will be collected and documented in the CRF at screening.

5.4 Other restrictions

Not applicable.

6 Treatment

6.1 Study treatment

Details on the requirements for storage and management of study treatment, and instructions to be followed for subject numbering, prescribing/dispensing and taking study treatment are outlined in the Pharmacy Manual.

Corporate Confidential Information

6.1.2 Additional study treatment

No additional treatment beyond investigational drug and control drug are included in this trial.

6.2 Treatment arms

Patients will be assigned to one of the following 2 treatment arms in a ratio of 1:1:

- LLG783 (**CCI**)
- Placebo (0 mg/vial)

6.3 Treatment assignment and randomization

At the randomization visit, all eligible patients will be randomized via Interactive Response Technology (IRT) to one of the treatment arms. The investigator or delegate will contact the IRT after confirming that the patient fulfills all the eligibility criteria. The IRT will assign a randomization number to the patient, which will be used to link the patient to a treatment- arm. The randomization number will not be communicated to the caller.

The randomization number is only used to identify which treatment the patients have been randomized to receive. The Subject number assigned to a patient at screening remains the unique identifier for the patient throughout the study. For information on subject numbering, please see ‘Subject numbering’ section in the SOM.

The randomization numbers will be generated using the following procedure to ensure that treatment assignment is unbiased and concealed from subjects and investigator staff. A patient randomization list will be produced by the IRT provider, or by a delegate under their supervision, using a validated system that automates the random assignment of subject numbers to randomization numbers. These randomization numbers are linked to the different treatment arms.

The randomization scheme for patients will be reviewed and approved by a member of the Novartis Randomization Office.

Follow the details outlined in the SOM regarding the process and timing of treatment assignment and randomization of patients.

